5.2 General Concomitant Medication and Supportive Care Guidelines

5.2.1 Steroid therapy.

For patients on systemic steroids, a steroid taper will be attempted 6 to 8 weeks after starting on protocol for those patients responding to therapy. Steroid taper will be performed at a maximal approximate rate of 10% (of starting dose) decrease per week. Once patients are on the equivalent prednisone dose of 0.5 mg/kg/day, taper will consist of decreasing the dose on an every other day schedule. The total decrease should remain equivalent to a maximum of approximately 10% decrease per week as tolerated. For worsening of cGVHD symptoms during steroid taper, a steroid pulse and dose increase will be allowed and subsequent taper attempted. For example, a typical steroid pulse of the equivalent to 1-2 mg/kg for 5-7 days with subsequent taper is acceptable. Steroid pulses require PI or LAI approval. Greater than 1 steroid pulse per 3 month period is considered disease progression. For patients on corticosteroids, consideration will be given to H2 blockade or other gastrointestinal protective agents.

5.2.2 Other immunosuppressants

Patients on a stable dose of calcineurin inhibitors (e.g. tacrolimus or cyclosporine) or other immunosuppressants (e.g. mycophenolate or sirolimus) will continue on these agents with the intent to wean if possible after steroids are tapered.

5.2.3 Infectious disease guidelines

Infection Prophylaxis: Routine measures to prevent infection in accordance with NIH Allogeneic Stem Cell Transplantation guidelines should be employed (<http://intranet.cc.nih.gov/bmt/clinicalcare/guidelines.shtml>).

5.2.4 Concomitant drug interactions

Because there is a potential for interaction of imatinib mesylate with other concomitantly administered drugs through the cytochrome P450 system, the case report form must capture the concurrent use of all other drugs, over-the-counter medications, or alternative therapies. The Principal Investigator should be alerted if the patient is taking any agent known to affect or with the potential to affect selected CYP450 isoenzymes.

Use of the following concurrent medications is prohibited and must be discontinued at least two weeks prior to starting therapy (recommendations adapted from Thomson Reuters Micromedex®):

- a) 1. Alfuzosin Interaction: an increase in alfuzosin exposure
 - b) Summary: Alfuzosin should not be coadministered with potent inhibitors of cytochrome P450 3A4, such as imatinib, because alfuzosin exposure may be increased, (2008; Prod Info GLEEVEC(R) oral tablets, 2007).
 - c) Severity: moderate
 - d) Clinical Management: The concomitant use of alfuzosin and imatinib is not recommended. Pulse and blood pressure monitoring may be necessary.
 - e) Mechanism: inhibition of cytochrome P450 3A4-mediated metabolism of alfuzosin by imatinib
2. Aprepitant
 - a. Interaction: elevated imatinib plasma levels
 - b. Summary: Aprepitant is a weak-to-moderate (dose-dependent) inhibitor cytochrome P450 3A4 and could moderately inhibit the metabolism of imatinib, resulting in elevated plasma concentrations of imatinib and potentially increased imatinib side effects.
 - c. Severity: major
 - d. Clinical Management: If coadministered, consider monitoring the patient for the following imatinib-related adverse effects: delayed myelosuppression, nausea, vomiting, and diarrhea.
 - e. Mechanism: inhibition of cytochrome P450 3A4-mediated metabolism of imatinib by aprepitant
3. Carbamazepine
 - a) Interaction: decreased plasma levels of imatinib
 - b) Summary: Concurrent administration of imatinib and carbamazepine may result in a significant decrease in exposure to imatinib due to induction of CYP3A4-mediated imatinib metabolism. Caution is advised when these two agents are coadministered. Alternatives to carbamazepine, with less enzyme induction potential, should be considered. When imatinib is used concurrently with carbamazepine, consider an increase in imatinib dose by at least 50% to maintain therapeutic efficacy and monitor clinical response closely (Prod Info GLEEVEC(R) oral tablets, 2005).

- c) Severity: major
 - d) Clinical Management: Consider using alternatives to carbamazepine with less enzyme induction potential. However, if imatinib is used concurrently with carbamazepine, consider an increase in imatinib dose by at least 50% to maintain therapeutic efficacy and monitor clinical response closely.
 - e) Mechanism: induction of cytochrome P450 3A4-mediated metabolism of imatinib by carbamazepine
- a) 4. Clarithromycin Interaction: increased plasma levels of imatinib
- b) Summary: Caution is recommended when administering imatinib with cytochrome P450 3A4 inhibitors such as clarithromycin as they may decrease the metabolism and increase concentrations of imatinib (Prod Info GLEEVEC(R) oral tablets, 2005). Monitor patients for signs of imatinib dose-related adverse events (fluid retention/weight gain, nausea and vomiting, neutropenia).
 - c) Severity: moderate
 - d) Clinical Management: Caution is recommended when administering imatinib with inhibitors of the cytochrome P450 3A4 family, such as clarithromycin. Monitor patients for signs of imatinib dose-related adverse events (fluid retention/weight gain, nausea and vomiting, neutropenia).
 - e) Mechanism: inhibition of cytochrome P450 3A4 metabolism of imatinib by clarithromycin

5. Eletriptan

- a) Interaction: increased eletriptan exposure
- b) Summary: Increased exposure to eletriptan may be expected when eletriptan is used concomitantly with imatinib. Eletriptan should not be used within 72 hours of drugs that have demonstrated potent cytochrome P450 3A4 inhibition, such as imatinib (Prod Info Relpax(R), 2002; Prod Info Gleevec(R), 2002).
- c) Severity: moderate
- d) Clinical Management: Eletriptan should not be used within at least 72 hours of treatment with imatinib, a potent cytochrome P450 3A4 inhibitor. Pulse, blood pressure, and ECG monitoring may be necessary.
- e) Mechanism: inhibition of cytochrome P450 3A4-mediated metabolism of eletriptan by imatinib

6. Erythromycin

- a) Interaction: increased plasma levels of imatinib
- b) Summary: Caution is recommended when administering imatinib with cytochrome P450 3A4 inhibitors such as erythromycin as they may decrease the metabolism and increase concentrations of imatinib (Prod Info GLEEVEC(R) oral tablets, 2005). Monitor patients for signs of

imatinib dose-related adverse events (fluid retention/weight gain, nausea and vomiting, neutropenia).

- c) Severity: moderate
- d) Clinical Management: Caution is recommended when administering imatinib with inhibitors of the cytochrome P450 3A4 family, such as erythromycin. Monitor patients for signs of imatinib dose-related adverse events (fluid retention/weight gain, nausea and vomiting, neutropenia).
- e) Mechanism: inhibition of cytochrome P450 3A4 metabolism of imatinib by erythromycin

7. Pimozide

- a) Interaction: increased plasma levels of pimozide
- b) Summary: Plasma concentrations of pimozide may be altered when coadministration with imatinib. Caution should be utilized when administering imatinib with cytochrome P450 3A4 substrates, such as pimozide, that have narrow therapeutic windows (Prod Info Gleevec(TM), 2002).
- c) Severity: moderate
- d) Clinical Management: Caution is recommended when administering imatinib with pimozide, a cytochrome P450 3A4 substrate with a narrow therapeutic window.
- e) Mechanism: inhibition of cytochrome P450 3A4 metabolism of pimozide by imatinib

8. St John's Wort

- a) Interaction: increased imatinib clearance
- b) Summary: In a pharmacokinetic study, concomitant use of imatinib and St. John's Wort resulted in significantly increased clearance of imatinib. Caution is advised when these two agents are coadministered. Alternatives to St. John's Wort, with less CYP450 enzyme induction potential, should be considered. However, if imatinib is used concurrently with St. John's Wort, consider an increase in imatinib dose by at least 50% to maintain therapeutic efficacy and monitor clinical response closely (Prod Info GLEEVEC(R) oral tablets, 2005).
- c) Severity: major
- d) Clinical Management: Coadministration of imatinib and St. John's Wort, a CYP3A4 inducer, may result in a significant reduction in exposure to imatinib. Caution is advised when these two agents are coadministered. Consider using alternatives to St. John's Wort with less enzyme induction potential. However, if imatinib is used concurrently with St. John's Wort, consider an increase in imatinib dose by at least 50% to maintain therapeutic efficacy and monitor clinical response closely.
- e) Mechanism: induction of cytochrome P450 3A4 metabolism of

imatinib by St. John's Wort

9. Warfarin

- a) Interaction: increased risk of bleeding
- b) Summary: Imatinib is a moderately potent inhibitor of the cytochrome P450 isoenzymes CYP2C9, CYP2D6 and CYP3A4, for which warfarin is a substrate. Concurrent treatment with imatinib and warfarin may increase the bioavailability of warfarin, thereby increasing the risk of bleeding (Prod Info GLEEVEC(R) oral tablet, 2005). Low molecular weight heparins or standard heparin may be considered as thromboprophylactic alternative, due an apparent absence of interaction between imatinib and these agents. Since thrombocytopenia is an adverse event consistently associated with imatinib therapy, caution is advised with any concomitant anticoagulant/antithrombotic therapy given with imatinib.
- c) Severity: major
- d) Clinical Management: Patients requiring anticoagulant therapy during treatment with imatinib should receive a low-molecular weight or standard heparin. If warfarin is used, closely monitor coagulation parameters (International Normalized Ratio, activated clotting time) for any patient receiving concurrent treatment with imatinib.
- e) Mechanism: competitive inhibition of isoenzyme CYP3A4 and imatinib-provoked inhibition of CYP2C9 and CYP2D6-mediated warfarin metabolism

Secondary to P450 3A4-mediated interaction, use of the following concurrent medications is allowable, with the following precautions:

1. P450 3A4 inducers: Induction of cytochrome P450 3A4-mediated metabolism of imatinib by potent inducers causes decreased exposure to imatinib. When imatinib is used concurrently with potent P450 3A4 inducers, imatinib dose will be increased by 50% to maintain therapeutic efficacy. Patients will be monitored closely for toxicity. The following medications are considered potent inducers of P450 3A4: Phenobarbital, Phenytoin, and Rifampin.
2. P450 3A4 inhibitors: Inhibition of cytochrome P450 3A4 affects the metabolism of imatinib causing increased plasma levels of imatinib. Patients will be monitored carefully while on the following medications: itraconazole, ketoconazole, posaconazole, voriconazole and fluconazole. However, routine dose reduction will not be employed due to the lower dosing (100-200mg daily) compared with typical imatinib therapy (400mg daily). Grapefruit juice should not be consumed while on therapy.
3. Other drug–drug interactions: Imatinib mesylate is an inhibitor of CYP3A4, therefore the following precautions should be followed:

- a. Cyclosporine – interaction effect caused by inhibition of CYP3A4-mediated metabolism of cyclosporine by imatinib, leads to increased plasma levels of cyclosporine. Must closely monitor CSA levels on imatinib and when imatinib is discontinued, adjust dosing to therapeutic window as indicated.
- b. Levothyroxine – imatinib causes decreased levothyroxine effectiveness and worsening of hypothyroidism. Closely monitor thyroid hormone levels while receiving imatinib and when discontinued, adjust as indicated.
- c. Simvastatin - Concurrent administration of simvastatin and imatinib resulted in 2- and 3.5-fold mean increases in C_{max} and AUC values of simvastatin, respectively (Prod Info GLEEVEC(R) oral tablets, 2005). Caution is advised when these two agents are coadministered. Monitor patients for increased simvastatin side effects (rhabdomyolysis, myopathy).
- d. Patients using other CYP3A4 substrates including sirolimus and tacrolimus should be monitored closely for toxicity while on imatinib mesylate therapy and levels closely followed.

5.2.5 Supportive care

Supportive care will include standard infection prophylaxis, anti-emetics, CMV surveillance at follow-up, topical care, pulmonary toilette with inhalers, physical therapy, nutritional, and psychosocial support. Anti-emetic therapy should not include dexamethasone or other corticosteroids. Support care as per recommendations in the NIH Consensus Project Report by the Ancillary Therapy and Supportive Care Working Group [34].

5.3 Duration of Therapy

Patients will be evaluated weekly for side effects for a minimum of one month or until stable dose is achieved. Patients will be evaluated monthly thereafter for safety monitoring and every 3 months for disease response. The primary endpoint assessment will occur at 6 months. Responsive patients will be provided continued treatment for up to 6 months following maximal response up to a maximum of 24 months. While on study, patients will need to return to the clinical center for evaluations at the 1 month, 3 month and 6 month time points, and every 6 months thereafter. Interim evaluations may be done by their primary physician. Patients who progress on treatment will be removed from the study.

In the absence of treatment delays due to adverse event(s), treatment will continue until the primary endpoint (6 months). Patients who are continuing to show a response will be treated up to 2 years or until one of the following criteria applies:

- Disease progression after 8 weeks, or no evidence of response at 6 months,

- Intercurrent illness that prevents further administration of treatment,
- Unacceptable adverse event(s),
- Patient decides to withdraw from the study,
- General or specific changes in the patient's condition render the patient unacceptable for further treatment in the judgment of the investigator,
- Recurrent malignancy
- Inability to comply with study requirements or PI discretion
- Patients requiring additional systemic therapy for control of GVHD will be taken off study after discussion with the PI or LAI.

5.4 Duration of Follow Up

Patients will be followed every three months for 1 year by telephone interview after discontinuing treatment or until death, whichever occurs first. Patients removed from treatment for unacceptable adverse events will be followed until resolution or stabilization of the adverse event. Once there is resolution of adverse events, patients will be removed from study.

5.5 Criteria for Removal from Study

Patients will be evaluated weekly for side effects for a minimum of one month after a stable dose is achieved. Patients will be evaluated monthly thereafter for safety monitoring and every 3 months for response. Patients will be removed from study when any of the criteria listed in Section 5.3 applies. Primary endpoint assessment will occur at 6 months. Patients will be treated for 6 months following maximal response up to a maximum of 24 months. Patients will be followed for 1 year after discontinuing study treatment. Therefore the maximum a patient will remain on study is 3 years. The reason for study removal and the date the patient will be documented in the Case Report Form.

Authorized staff must notify Central Registration Office (CRO) when a subject is taken off-study. An off-study form from the web site (<http://home.ccr.cancer.gov/intra/eligibility/welcome.htm>) main page must be completed and faxed to [contact].

6 DOSING DELAYS/DOSE MODIFICATIONS

Treatment modifications: All dose modifications must be discussed with the PI or LAI. This study will utilize version 4.0 of the NCI Common Terminology Criteria for Adverse Events (CTCAE) (<http://ctep.cancer.gov/reporting/ctc.html>) for toxicity and adverse event reporting.

Only those adverse events deemed possibly, probably, or definitely related to imatinib mesylate will be used in the definition of DLT. Events that are considered disease related will not be considered dose limiting. Expected pre-existing or concurrent manifestations of cGVHD or systemic steroid therapy may include the following examples: fatigue, colitis, cushingoid appearance, anorexia, xerostomia, nausea, taste alteration, arthritis, fibrosis, myositis, osteonecrosis, osteopenia, dry eye, watery eye, pain, dyspnea, vaginal dryness, skin atrophy, alopecia, hyperpigmentation, skin dryness, hypopigmentation, nail changes, photosensitivity, pruritus, rash, and ulcers. Any of the above symptoms newly presenting after initiation of imatinib mesylate must be carefully evaluated for attribution, i.e. new skin rash will be biopsied to determine drug reaction versus GVHD.

6.1 Dose reduction for adverse events

Adult patients receiving 200 mg daily or pediatric patients receiving 130 mg/m² who require dose reduction for adverse events will have their dose reduced to 100 mg (or 65 mg/m²). A second dose reduction to 50 mg daily is allowed for patients on potent CYP3A4 inhibitors. Patients with impaired renal function receiving 100mg daily who require a dose reduction for adverse events will have their dose reduced to 50mg daily. Treatment and dose reductions will be based on eGFR and not on serum creatinine for patients with moderate renal dysfunction.

Dose Modification Table for Non-hematologic and Hematologic Toxicities

Adverse Event	CTCAE 4.0 Grade/Attribution	Protocol Action
Non-hematologic toxicity (LFTs and eGFR [^] excluded)	Grade 2 >7 days that is probably or definitely related to imatinib.	Hold study drug; *If toxicity resolves to \leq grade 1 or baseline within 14 day days: restart drug at same dose level.
Non-hematologic toxicity (LFTs and eGFR [^] excluded)	Same grade 2 recurs that is probably or definitely related to imatinib.	Hold study drug; *If toxicity resolves to \leq grade 1 or baseline within 14 day days: decrease dose by 1 dose level. **If toxicity does NOT resolve to \leq Grade 1 or baseline within 14 day days: patient comes off study.
Non-hematologic toxicity (LFTs and eGFR [^] excluded)	Same grade 2 recurs after dose reduction that is probably or definitely related to imatinib.	Patient comes off study. Exception: patients on a CYP3A4 inhibitor [which allows a second dose reduction].

Adverse Event	CTCAE 4.0 Grade/Attribution	Protocol Action
Non-hematologic toxicity (LFTs and eGFR [^] excluded)	Grade 3 that is probably or definitely related to imatinib.	Hold study drug; *If toxicity resolves to \leq grade 1 or baseline within 14 day days: decrease dose by 1 dose level. **If toxicity persists >14 days or if Grade 3 recurs after dose reduction: patient comes off study.
Non-hematologic toxicity (LFTs and eGFR [^] excluded)	Grade 4 that is probably or definitely related to imatinib.	Patient comes off study
Non-hematologic toxicity: LFTs ; eGFR [^]	Grade 2	No dose adjustment.
Non-hematologic toxicity: LFTs; eGFR [^]	Grade 3 >7 days that is probably or definitely related to imatinib.	Hold study drug; *If toxicity resolves to baseline within 14 day days: restart drug at same dose level.
Non-hematologic toxicity: LFTs; eGFR [^]	Same grade 3 recurs that is probably or definitely related to imatinib.	Hold study drug; *If toxicity resolves to baseline within 14 day days: decrease dose by 1 dose level. **If toxicity does NOT resolve to baseline within 14 day days: patient comes off study.
Non-hematologic toxicity: LFTs; eGFR [^]	Grade 4 that is probably or definitely related to imatinib.	Patient comes off study
Hematologic: Cytopenias	Grade 2	No dose adjustment.
Hematologic: Neutrophil or Platelet toxicity	Grade 3 on two sequential evaluations within 7 days that is probably or definitely related to imatinib.	Hold study drug; *Until counts recover to a grade 2 then restart at same dose level.

Adverse Event	CTCAE 4.0 Grade/Attribution	Protocol Action
Hematologic: Neutrophil or Platelet toxicity	Same grade 3 recurs that is probably or definitely related to imatinib.	Hold study drug; *Until counts recover to a grade 2 then decrease dose by 1 dose level.
Hematologic: Neutrophil or Platelet toxicity	Same grade 3 recurs after dose reduction that is probably or definitely related to imatinib.	Patient comes off tudy.
Hematologic: Neutrophil or Platelet toxicity	Grade 4	*If toxicity resolves to < Grade 2 within 14 day days: Decrease dose by 1 dose level. **If toxicity does NOT resolve to < grade2 within 14 day days: Patient comes off study.
Hematologic: Neutrophil or Platelet toxicity	Same grade 4 recurs	Patient comes off study.

^ = **Patients with moderate renal dysfunction.** Patient with mild renal dysfunction or normal renal function at baseline will receive dose adjustment based on the standard guidelines for other non-hematologic provided in Table 1.

Exceptions to the above treatment modifications:

1. Alopecia.
2. Grade 2 or 3 low electrolyte levels in patients with chronic low levels of the same electrolyte. Such individuals should receive supplementation and any worsening of levels should be discussed with the PI to determine whether to consider dose limiting.
3. Hypocalcemia toxicity grade should be assigned based on the calcium level corrected for degree of hypoalbuminemia according to the following formula: albumin ↓ 1 gram/dL: total calcium ↑ 0.2 mmol/L. Ionized calcium can also be used to assess toxicity.
4. Grade 3 fever.
5. Infection or neutropenic fever unless attributed to imatinib mesylate.
6. Lymphopenia any grade
7. Grade 3 hypertriglyceridemia or hypercholesterolemia.
8. Grade 3 non-life-threatening basal or squamous cell carcinoma of the skin. This patient population is predisposed to non-melanoma skin cancer due to chronic immunosuppression associated with cGVHD treatment.
9. Grade 2 fatigue

10. Grade 2 dry skin
11. Grade 2 albumin
12. Grade 2 or 3 asymptomatic CPK elevation with no evidence of rhabdomyolysis or cardiac myositis.
13. Grade 2 proteinuria
14. Grade 2 tinnitus
15. Grade 2 insomnia
16. Grade 2 rash
17. Grade 2 anorexia

Each treatment cycle should be no longer than 28 days. Doses withheld while recovering from toxicity should not be made up.

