5 TREATMENT PLAN

5.1 Imatinib Mesylate Administration

This is an open-label pilot study of oral imatinib mesylate for ScGVHD. Adult patients will receive 100 mg imatinib mesylate daily and pediatric patients will be dosed at 65 mg/m² daily (100 mg maximum) for 28 days. If tolerated, after 28 days, adult patients will be increased to 200 mg daily and pediatric patients will be increased to 130 mg/m² (200 mg maximum). If the 100mg (or 65mg/m²) dose is not tolerated due to unacceptable toxicity within the first 28 days despite following the dosing delay guidelines (section 6.0), the drug will be discontinued, except for patients taking 100mg daily who are also on potent CYP3A4 inhibitors. This group will be allowed dose reduction to 50mg. Children with a BSA < 0.97 (starting dose 50mg) who do not tolerate the drug during the first 28 days will be taken off study because dose reduction below 50mg is not possible with the 100mg tablets. Treatment cycles are continuous 28-day cycles with no rest period between cycles.

Imatinib mesylate is supplied as 100 mg tablets. Adult patients will initially receive 100 mg imatinib mesylate daily and pediatric patients will be dosed at 65 mg/m² daily (100 mg maximum, see nomogram below). After 1 month, adult patients will increase to 200 mg daily and pediatric patients will receive 130 mg/m² daily. Individual patient dosages will be rounded to the nearest 50 mg increment. Tablets are scored and the 100 mg tablets may be cut into achieve 50 mg dosing. According to the package insert, tablets may be dispersed in a glass of water or apple juice, stir until disintegrated and administer immediately. Since no long-term stability data are available, the administration of imatinib suspension should not be delayed. Patient should take drug with a meal and a large glass of water (patients who dissolve their tablets in liquid do not need to drink additional water). See Appendix Q for patient instructions.

The product labeling for imatinib mesylate provides dosing guidelines for patients with renal dysfunction, as defined by the following criteria (Prod Info GLEEVEC® oral tablets, 2010):

Renal Dysfunction Definitions (based on Product labeling)

Mild CrCL = 40-59 mL/min

Moderate CrCL = 20-39 mL/min

Severe CrCL = <20 mL/min

Mild renal dysfunction

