The product labeling cautions that dose reduction may be needed at higher dosages of imatinib mesylate for patients with mild renal dysfunction. However, because patients on this protocol receive a low starting dose (100mg), dose adjustment will not be made for patients with mild renal dysfunction (creatinine clearance ≥ 40 ml/min).

Moderate renal dysfunction

As recommended by the product labeling guidelines (Prod Info GLEEVEC® oral tablets, 2010), patients with moderate renal dysfunction will decrease the starting dose by 50%. Therefore, adult patients and pediatric patients with BSA ≥ 0.97 will initially receive 50mg imatinib mesylate daily. After 1 month, adult patients and pediatric patients with BSA ≥ 0.97 and moderate renal dysfunction will increase to 100 mg daily if tolerated. Treatment and dose reductions will be based on estimated glomerular filtration rate (eGFR) and not on serum creatinine for patients with moderate renal dysfunction.

Children with a BSA < 0.97 (normal starting dose 50mg) with moderate renal dysfunction (creatinine clearance 30 -39ml/min) are ineligible because dose reduction is not possible below 50 mg.

Adult and pediatric patients with renal dysfunction between 20-30ml/min and with severe dysfunction (<20 ml/min) are not eligible for treatment.

Dose Nomogram for Pediatric Patients

65 mg/m ² /d		130 mg/m ² /d	
BSA [m²]	Dose [mg]	BSA [m²]	Dose [mg]
		0.38 – 0.57	50
0.58 – 0.96	50	0.58 – 0.96	100
≥ 0.97	100	0.97 – 1.34	150
		≥ 1.35	200

Patients receiving concomitant CYP3A4 inducers will have the starting dose of imatinib increased by 50%. The starting dosing of imatinib will be 150 mg/day for adult patients and 100 mg/m²/day for pediatric patients on concomitant CYP3A4 inducers. According to the package insert, tablets may be dispersed in a glass of water or apple juice, stir until disintegrated and administer immediately. Patients receiving concomitant CYP3A4 inhibitors (itraconazole, ketoconazole, posaconazole, voriconazole and fluconazole) will be monitored closely for toxicity, but routine dose reduction will not be employed.

Treatment will be administered on an outpatient basis. Reported adverse events and potential risks are described in Section 7. Appropriate dose modifications for imatinib mesylate are described in Section 6. No investigational or commercial agents or therapies other than those described below may be administered with the intent to treat the patient's cGVHD.

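### Section 6.1's text and its dose-modification table disagree on which patients taking CYP3A4 inhibitors may step down from 100 mg to 50 mg

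*Combined protocol and SAP*

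**What the plan says.** Three places in the protocol govern the step from 100 mg to 50 mg.

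- **Section 5.1**, for patients who do not tolerate the starting dose in the first 28 days: "the drug will be discontinued, except for patients taking 100mg daily who are also on potent CYP3A4 inhibitors". Those excepted patients may go to 50 mg.
- **Section 6.1, text**, for patients already reduced from 200 mg: "A second dose reduction to 50 mg daily is allowed for patients on potent CYP3A4 inhibitors". For renal patients it adds: "Patients with impaired renal function receiving 100mg daily who require a dose reduction for adverse events will have their dose reduced to 50mg daily".
- **Section 6.1, table.** The row for grade 2 non-hematologic toxicity recurring after reduction removes the patient, then adds: "Exception: patients on a CYP3A4 inhibitor [which allows a second dose reduction". The grade 3 non-hematologic row says "if Grade 3 recurs after dose reduction: patient comes off study". The neutrophil/platelet row headed "Same grade 3 recurs after dose reduction that is probably or definitely related to imatinib" also removes the patient, as does the row for recurrent grade 4 neutrophil or platelet toxicity. None of these last three rows carries an exception.

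Section 5.2.4 labels its list of permitted CYP3A4 inducers as potent. It names five permitted inhibitors (itraconazole, ketoconazole, posaconazole, voriconazole and fluconazole) without saying which are potent.

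Section 14.1.1 sets the tolerability rule: acceptable if at least 8 of the first 10 patients in the new cohort tolerate the drug. It describes success in two ways, as lasting on drug until the three-month efficacy assessment and as tolerating 200 mg.

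**The concern.** The text and the table differ on two things: which toxicities the exception covers, and which inhibitors qualify a patient for it. The case is foreseeable, because the azoles are expressly permitted on study. For such a patient with recurrent toxicity at 100 mg, the provision applied decides whether treatment continues, and whichever action is taken departs from some part of the protocol.

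Tolerability of 200 mg is a primary objective, judged on ten patients with room for two failures. If removal and continuation at a lower dose are scored differently, the choice of provision feeds into that result.

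A second ambiguity concerns renal patients. Section 6.1 does not say whether its renal sentence includes mild dysfunction, which Section 5.1 defines as creatinine clearance of 40 to 59 mL/min.

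**Working it through.** **Step 1. The provisions side by side.** Take a patient reduced from 200 mg to 100 mg whose toxicity, of the attribution the table requires, recurs.

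| Inhibitor and recurrent toxicity | 6.1 text | 6.1 table | Agree? |
|---|---|---|---|
| Potent; grade 2 non-hematologic | 50 mg allowed | 50 mg allowed | Yes |
| Potent; grade 3 non-hematologic | 50 mg allowed | Removed | No |
| Potent; grade 3 neutrophil/platelet | 50 mg allowed | Removed | No |
| Potent; grade 4 neutrophil/platelet | 50 mg allowed | Removed | No |
| Not potent; grade 2 non-hematologic | Not covered | 50 mg allowed | No |
| Not potent; the three grade 3 or 4 cases above | Not covered | Removed | Yes |

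Section 5.1 agrees with the 6.1 text in requiring a potent inhibitor. Because the azoles are ungraded, a site cannot tell from the protocol which rows apply to its patient.

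**Step 2. The renal sentence.** Section 5.1 says "dose adjustment will not be made for patients with mild renal dysfunction", so those patients start at 100 mg. For the moderate group it starts at 50 mg, and after one month patients with "moderate renal dysfunction will increase to 100 mg daily if tolerated".

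- If the 6.1 sentence means moderate dysfunction only, these patients reach 100 mg after the 28-day window in 5.1 has closed, and there is no conflict.
- If it includes mild dysfunction, a patient on no inhibitor who fails 100 mg in month 1 is discontinued under 5.1 and reduced under 6.1.

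**Step 3. The plan's own figures.** Section 14.1.1 gives n = 10, a cut-off of 8, and true rates of 90% and 50%. With X binomial:

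- At 0.90: P(X ≥ 8) = 45(0.9⁸)(0.1²) + 10(0.9⁹)(0.1) + 0.9¹⁰ = 0.1937 + 0.3874 + 0.3487 = 0.9298. The plan states 93.0%.
- At 0.50: (45 + 10 + 1)/1024 = 0.0547. The plan states 5.5%.

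Both reproduce.

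**Step 4. When the conflict reaches this rule.** If success means tolerating 200 mg, a patient at 50 mg fails whether kept or removed. If success means reaching the three-month assessment on drug, keeping the patient gives a success and removal before that visit gives a failure. Escalation, toxicity, reduction and recurrence must all fall before month 3. A patient who fails 100 mg in month 1 never escalates to 200 mg, so the renal question does not enter here.

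**Step 5. Size under the second reading.** Assume k of the ten patients have their status fixed by the provision applied, and the other 10 − k tolerate independently at rate p. No figure in the documents supports a value of k; 1 and 2 are illustrations. The pass probability is P(Y ≥ 8) if the k patients are failures and P(Y ≥ 8 − k) if successes, with Y binomial on 10 − k.

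| k | p | Fixed as failures | Fixed as successes |
|---|---|---|---|
| 1 | 0.90 | 77.5% | 94.7% |
| 1 | 0.50 | 2.0% | 9.0% |
| 2 | 0.90 | 43.0% | 96.2% |
| 2 | 0.50 | 0.4% | 14.5% |

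For k = 1 and p = 0.90: 9(0.9⁸)(0.1) + 0.9⁹ = 0.3874 + 0.3874 = 0.7748. Adding 36(0.9⁷)(0.1²) = 0.1722 gives 0.9470. That 17.2-point gap is the chance that exactly 7 of the other 9 tolerate, the only situation in which this one patient decides the verdict.

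**The case against.** The strongest defence is that text and table can be read together. The text is permissive, and the table may specify when the permission applies: after recurrent grade 2 toxicity but not after recurrent grade 3 or 4. The bracket in the table's exception may likewise refer back to the text and so import the restriction to potent inhibitors. Section 6 also requires every dose modification to be discussed with the PI or lead associate investigator.

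This harmonised reading is possible, but the protocol does not state it, and a reader who treats the text as the general rule reaches the opposite action. The required discussion limits inconsistent handling but supplies no rule to apply. Nothing in the defence says which azoles are potent.

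On the renal sentence the defence is stronger. The next sentence of 6.1 concerns moderate dysfunction, and the table footnote places mild dysfunction with normal function under the standard non-hematologic guidelines. A reader might infer a firm contradiction with 5.1; the documents do not support that, because the natural reading is moderate dysfunction only. What stands is that 6.1 does not say so.

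A reader might also infer that removal costs the trial its range-of-motion data. Section 11.1.3 asks for that assessment, if possible, when a patient comes off treatment for any reason, and Section 14.1 replaces patients not evaluable at three months, within the 13-patient allowance. Removal can still change who is in the efficacy set.

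**Conclusion.** The conflict between the 6.1 text and the 6.1 table holds. It covers three grade 3 or 4 recurrence situations for patients on potent inhibitors and one grade 2 situation for patients on other inhibitors, and the ungraded azole list leaves the boundary between those groups undefined. The renal wording is an ambiguity, and a conflict only if mild dysfunction is included.

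A reader might infer that the contradiction by itself puts the tolerability conclusion in doubt. The documents do not support that. The effect needs the three-month reading of 14.1.1, a removal before month 3, and a trial sitting at the boundary between two and three failures. Nor is there support for treating a tenth of patients as reclassified. Lowering the true rate from 90% to 80% would cut the pass probability from 0.930 to 0.678, which is correct arithmetic on a proportion that the documents do not give. The affected group is narrow and its size unknown. The range of 77.5% to 94.7% for one assumed patient shows sensitivity and is not a forecast.

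The point merits correction mainly because it decides whether a foreseeable patient stays on drug.

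**What to change.** Reconcile Section 5.1, the 6.1 text and the 6.1 table:

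1. State once which patients the 50 mg step covers, naming the qualifying inhibitors and the renal category.
2. Make every recurrence row of the table agree with that statement, either by carrying the exception or by saying that it does not apply.
3. State in Section 14.1.1 whether a patient who reaches the three-month assessment on a reduced dose counts as tolerating.

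The sponsor decides which version of the dose rule applies; this review takes no view on it. The cost is protocol wording and table edits, with no new patients or procedures.
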